### **Introduction**

Gout is the most common inflammatory arthritis that affects 4% of U.S. adults (1) and 5% of Veterans.(2) Gout is more common in African-Americans(1) who have worse outcomes compared to Caucasians.(3) Medication adherence of >80% to urate-lowering therapy (ULT), the cornerstone of gout treatment, in the first year is only 37%.(4) This medication adherence for gout was the lowest as compared to medication adherence of 55-72% in six other chronic disease, including hypertension, hypothyroidism, type 2 diabetes, seizure disorders, hypercholesterolemia and osteoporosis.(4). We recently found that the total charges for admissions for gout as primary or secondary diagnosis for hospital admission increased from \$14.3 billion/year in 2009 to \$18 billion/year in the U.S. in 2012 based on national inpatient sample, a U.S. representative study (6). Gout is common in Veterans, affecting up to 5% of all Veterans.(2) Thus, gout-related healthcare utilization and cost, especially emergency department and inpatient costs, constitute a huge burden for the VA. A recent study found that 89% of gout hospitalizations were preventable, many related to poor medication adherence (5). This indicates that a significant proportion of this health care costs and patient suffering due to gout is likely preventable.

Compared to Caucasians, AAs have lower rates of ULT prescription (42% vs. 80%) and 1.86-times odds of inadequate ULT adherence (<0.80, 64% vs. 77%).(7, 8) Optimal ULT adherence is key to gout management, since it improves the ability to achieve the target serum urate <6 mg/dl, and is associated with lower medical care costs and risk of gout flares.(11-13) This treatment goal is also recommended by gout treatment guidelines.(9, 10) A patient-centered intervention is highly appropriate in gout, since a lack of knowledge and misconceptions regarding ULT use are common among patients,(14-16) similar to other chronic conditions.(17, 18) Thus, gout is a very useful test case for chronic symptomatic diseases.

With VA HSR&D pilot funding (PPO 14-111), we have completed the development of the storytelling intervention. The purpose of developing the Storytelling Intervention Video in the pilot study was to test it with our subsequent study, which is this fully funded HSR&D merit review. The veterans participating in the intervention video signed the HIPAA Authorization and consent for use of picture and voice. These documents stated that the video recordings will be "analyzed for effectiveness" (as stated in the video recording consent document). The proposed study is to analyze the effectiveness of the intervention video that will "disseminated to other gout patients" (as stated in both HIPAA and Video recording consent documents- **Appendix 1**-highlighted). We will determine the effectiveness of the intervention compared to usual care by conducting a 12-month multicenter randomized controlled trial (RCT) among 150 AA Veterans with gout with a ULT adherence of <0.80 at Birmingham VAMC (total 300 AA Veterans at the 3 proposed VA sites- Birmingham, St. Louis, and Philadelphia VA Medical Centers).

[figure not shown]
Our objective is to test the effectiveness of a patient-centered, culturally relevant narrative intervention, or "storytelling," based on the solid conceptual foundation of the narrative communication theory(19) and the constructs of the Health Belief Model,(20) (HBM) to improve medication adherence and outcomes in chronic diseases among African-Americans (AA), using gout as an example. Gout is a chronic disease associated with chronic symptoms and disability interrupted by intermittent acute flares, similar to Chronic Obstructive Pulmonary Disease (COPD) and Congestive Heart Failure (CHF) that leads to joint destruction if not treated appropriately. Due to the intermittently symptomatic nature of chronic conditions patients, often don't perceive disease severity and susceptibility to disease complications, and, therefore, may not balance the barriers and benefits to medication adherence.(21) Storytelling in the patients' own voice has the power to directly and more effectively confront a patient's barriers to medication adherence, reinforce the benefits and provide useful cues to action.(22) Storytelling promotes patient engagement when the patient identifies with the storyteller and can lead to a patient's recognition of the need to treat the condition and improve health outcomes, as

shown by a meaningful improvement in blood pressure in a recent clinical trial in AA with hypertension.(23) The success of this project, combined with other published data, will represent a major step toward demonstrating the effectiveness of storytelling to improve medication adherence in chronic diseases and will address **two VA research priority areas**, i.e., health care disparities and health care delivery.

Our **Specific Aims (SAs)** are to assess the effectiveness of a storytelling intervention in African-American Veterans with gout for:

- **SA1: Improving ULT adherence, directly measured by using MEMS (Medication Event Monitoring System) Caps** at 3, 6 and 9 months (assess intervention's effect) and 12 months (assess durability of effect),
- SA2: Improving Gout flare rate, patient satisfaction and target serum urate (sUA) <6 mg/dl achievement, as indirect measures of better ULT adherence and important gout outcomes. We will also explore the effect of storytelling on health-related quality of life (HRQOL), self-reported ULT adherence, alcohol ingestion, body mass index (BMI) and gout-related inpatient and emergency room utilization.

Figure 1 below shows the anticipated study flow diagram for this project. The primary aims are to study the effectiveness of novel storytelling on ULT adherence and patient outcomes in gout. In Aims 1 and 2, we will conduct a multicenter, parallel 2-arm, 12-month RCT comparing the storytelling intervention to usual care in African-American Veterans with gout. Patients in the storytelling intervention group will view the designed storytelling video and the usual care group will view a presentation on stress management for the same time duration (attention control), on an iPAD in the clinic during the baseline visit. Mailed DVDs to the enrolled patients at 2- and 4-months with additional storytelling clips will reinforce messages for behavioral change received during the baseline visit through storytelling videos; mailed DVDs to the attention control group will provide more information on stress management. MEMSCap (Aprex Corp., Fremont, California), a medication bottle cap with a microprocessor that records the occurrence and date and time whenever a patient opens a vial using integrated microcircuits, will be used as a measure of primary outcome of ULT adherence.(24) It will be dispensed at baseline visit and data downloaded at 6- and 12-month in-person visit. Patients will receive the first 90-day supply in special bottles with MEMSCap and be trained at the initial visit regarding the importance of MEMSCap and not to discard it but bring it to the 3-, 6-, 9- and 12-month clinic visits.

Methods
Study Population.

This is a prospective randomized study of AA Veterans with gout and low adherence to urate-lowering therapy (ULT), the cornerstone of gout treatment. The intervention being tested is a series of three videos shown at baseline, 2, and 4-months post-enrollment with follow up assessments completed at 3, 6, 9, and 12 months. We anticipate 150 Veterans to be enrolled from rheumatology and primary care clinics within the Birmingham VA Medical Center and its affiliated community-based outpatient clinics (CBOCs). Detailed patient recruitment plan is provided in **Appendix 2**, a flow chart (**Appendix 3**) and related details in **Appendix 4**. Data sources include administratively collected data from the electronic health record and the Corporate Data Warehouse (CDW) and inpatient/outpatient SAS files assessed through the VA informatics and Computing Infrastructure (VINCI) patient interviews, medication usage from MEMSCap, and a usual care blood draw to assess serum urate.

The storytelling intervention has been developed to be generalizable to all gout patients and thus we plan to recruit a representative sample at the Birmingham VA. Gout patients seen at referral clinics such as rheumatology are often selected for worse or more advanced disease and thus not representative of general patients with gout. Patients in primary care clinics are more representative and therefore, we plan to recruit across all Birmingham VA primary care clinics and rheumatology clinics.

## Study Run-in period:

We have learnt that medication adherence estmates based on the medication possesson rato (MPR) calculated from prescription refill data are imperfect, and vary substantially when based on 6, 9, or 12 month data. We will therefore have a study run-in period of 4, 8, or 12 weeks by patient choice during which we will determine medication adherence using the MEMScap device on patients who have been determined to have low gout medication adherence (<80%) calculated from pharmacy refill data. Only patients meeting the MPR <80% calculated using MEMScap data will be enrolled in the study and randomized. We will re-consider patients who fail the run-in for future enrollment in the study, when their medication possession ration decreases again.

The study run-in period also allows for a more time for the veterans to review the informed consent and to ask more questions, since veterans would have had from 1-3 months to review the consent form after having signed it, before entering the study.

### Intervention.

The intervention being tested is a series of three videos shown at baseline, 2, and 4 months post-enrollment. The baseline video will be shown at the Birmingham VA using VA-approved iPADs and the follow up videos will be distributed to patients as DVDs via mail. We chose the platform of touchscreen computer (e.g., iPAD) for the baseline video for two reasons: (1) the patients will be in the clinic for the baseline visit, and this would ensure that every patient gets the complete intervention in both groups at baseline; and (2) patients will be interacting with the touchscreen technology, which is the proposed platform for the future implementation. To ensure data security, the iPADs will be set up by the Office of Information Technology and will be encrypted prior to use by the study team personnel (FIPS 140-2).

Throughout the study, each video will either have the gout storytelling intervention with patient narrated stories and "Learn More" gout material in a patient's own voice or the stress management video. The duration of the videos is the same (15-20 minutes based on previous experience). DVDs will have new stories from our storytelling stars but will be similar to those presented at the baseline visit.

#### Outcomes.

- Primary outcome: Adherence to ULT as assessed directly with MEMSCap
- Secondary outcomes: Adherence to ULT as assessed indirectly by the following improved outcomes. These secondary outcomes will be assessed from patient surveys and by using the VA laboratory and

other relevant data collected by the CDW and inpatient/outpatient SAS files assessed through the (VINCI) database.

- a. Frequency of gout flares requiring treatment
- b. Patient satisfaction with treatment
- c. Achieving target serum urate (sUA) <6 mg/dl
- Exploratory outcomes will be assessed with surveys (HRQOL, self-reported ULT adherence, alcohol
  use) or from the VA database (BMI, healthcare utilization). Additional exploratory outcomes will focus
  on taking advantage of the detailed MEMS Caps data to examine the temporal relationships between
  medication adherence and specific research study events, e.g., the initial study visit, telephone survey,
  each DVD mailing, the 6 month research visit, and clinical events (e.g., an acute gout exacerbation or
  hospitalization).

Table 1: Summary of Primary and Secondary Outcomes and Outcome Measures to achieve SA1 and SA2			
Outcome	Assessments	Description	Clinically Meaningful Change
ULT adherence measured using MEMS*	3, 6, 9 and 12	Medication adherence to ULT measured using MEMSCap 	Absolute difference of 6% between groups representing a medium effect size of 0.40 (A smaller difference is unlikely to be meaningful)
Secondary outcomes (SA2)			
Number of Gout flares needing treatment	0, 1, 3, 6, 9 and 12	4-item patient-reported assessment of gout flare 	20% fewer patients with gout flares needing treatment
Patient Satisfaction with Medications Questionnaire (SATMED-Q)	0, 6 and 12	17-item patient-reported with six dimensions; 	Total score is between 5.9 and 13.4 and for SATMED-Q domain scores from 5.9 to 20.6, with most estimates close to 10.81
Serum urate <6 mg/dl	0 and 12	Serum urate standard biochemical assay 	20% more patients achieving target serum urate <6 mg/dl

\*Analyses of 12-month MEMS and secondary outcomes will indicate sustenance of treatment effects noted at 6-month

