## Study procedures at follow-up visits and data collection tools

Follow-up assessments will be done at 1-, 2-, 3-, 4-, 6-, 9-, and 12-months after the baseline visit. The 2- and 4-month visits will be completed via mail, the 3-, 6-, 9-, 12-month visits will be completed in-person lasting 30-60 minutes, and the 1- and 12-month assessments will be completed via phone lasting 15-minutes.

The primary time-point for analyses will be at 6-months. Assessments are kept short considering responder burden and to ensure study retention. Veterans will be provided with \$25 remuneration (VISA gift card or VA Form 10-7078 - Participant payment voucher) for completing the screening visit and each study assessment; an additional \$25 VISA gift card will be provided as VISA gift card or VA Form 10-7078 (Participant payment voucher) to those who perform both blood draws at baseline and 12-month end-of-study visits. If payment voucher is used, participant will bring this voucher to agent cashier to receive \$25 on the same day. 1-month follow-up will be done via a telephone-administered survey at the patient's convenience in their home, given that most assessments are patient-reported. This approach economizes on patient time compared to traditional gout RCTs, where patients are seen in the clinic every 1-3 months with visits lasting 1-3 hours including waiting time (plus travel time). 3-, 6- and 9-month visits will be in-person; MEMSCap data will be downloaded and other outcomes captured. To remind the patient of the follow-up assessments, a post-card (and emails, when applicable) will be mailed 1-week prior and phone call made 2-days prior to the follow-up. To minimize patient responder burden, Veterans are only completing assessments related to primary and select secondary study outcomes (including 4-item gout flare questionnaire at 6- and 12-month follow-up).

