The 12-month visit (end-of-study) will be in-person, similar to the baseline visit. The visit will be coordinated with a scheduled VA clinic visit, as much as possible. MEMSCap data will be downloaded and Veterans will complete a questionnaire assessing gout flares since last visit (including those requiring treatment) and patient satisfaction with treatment, as in 3-, 6- and 9-month follow-up. In addition, Veterans will be requested to get a blood draw for end-of-study sUA (secondary outcome)(32) and also complete GAQ as a gout-specific HRQOL measure and self-reported medication adherence questionnaire (exploratory outcomes). GAQ and sUA will be done only at 12-month follow-up (expected to take additional 30-minutes). Veterans unable to come to the study clinic for the 12-month visit will be offered sUA blood draw at their nearest CBOC (routine laboratory test) and the research associate will administer 12-month assessments via the phone interview.

Statistical Analysis.

- SA1: Improving ULT adherence, directly measured by using MEMS (Medication Event Monitoring System) Caps at 3, 6, 9 months (assess intervention's effect) and 12 months (assess durability of effect),
- SA2: Improving Gout flare rate, patient satisfaction and target serum urate (sUA) <6 mg/dl achievement, as indirect measures of better ULT adherence and important gout outcomes. We will also explore the effect of storytelling on health-related quality of life (HRQOL), self-reported ULT adherence, alcohol ingestion, body mass index (BMI) and gout-related inpatient and emergency room utilization.

For both Aims 1 and 2, descriptive statistics for demographics (age, race, income, marital status, time since diagnosis of gout) and clinical parameters (ULT adherence, # gout flares, satisfaction, serum urate, GAQ) will be examined. Given the two arm study design (storytelling vs. usual care), statistical procedures appropriate for two-group comparisons will be utilized to conduct crude as well as adjusted comparisons based upon the distributional nature of the outcome.

For the primary outcome of ULT adherence, an unadjusted analysis will be conducted using the two-sample ttest to compare ULT adherence across study arms at 3, 6, 9, and 12 months. Adjusted estimates of ULT adherence by study arm controlling for age, gender, income, alcohol, site, and other covariates will be conducted using ordinary least squares regression.

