Similar analyses will be conducted for the secondary outcomes defined in aim 2. When examining sUA level, analyses will also be adjusted for use of other medications that effect serum urate (diuretics, lipid-lowering agents, aspirin and angiotensin receptor blocking drugs etc.), BMI and alcohol use. For frequency of gout flares, analyses will also be adjusted for use of anti-inflammatory prophylaxis during initial ULT treatment. If the normality assumption is violated, nonparametric methods will be used, instead of the parametric tests.

Careful attention will be paid to the distributional assumptions for Poisson regression and methods to adjust for over-dispersion will be employed. Finally, separate logistic regression models will be used to measure treatment differences in the odds of achieving target serum urate <6 mg/dl and odds of healthcare utilization. To analyze the longitudinal data (1-, 3-, 6-, 9- and 12-months), we will use mixed linear models for ULT adherence (continuous outcome) and generalized estimating equations for target serum urate < 6 mg/dl, to analyze temporal relationships between the delivery of the intervention and medication adherence. All analyses will be guided by intent-to-treat analysis principles.

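### The flare questionnaire schedule differs between three places in the protocol, and the flare analysis names neither baseline flares nor observation time (secondary outcome, minor priority)

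*Combined protocol and SAP*

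**What the plan says.** **Schedule.** In the Outcomes section, the flare row of Table 1 describes a "4-item patient-reported assessment of gout flare" at months 0, 1, 3, 6, 9 and 12. The section on follow-up procedures explains that assessments are kept short and adds "including 4-item gout flare questionnaire at 6- and 12-month follow-up". The description of the 12-month visit refers to a "questionnaire assessing gout flares since last visit (including those requiring treatment) and patient satisfaction with treatment, as in 3-, 6- and 9-month follow-up". The same section also states "1-month follow-up will be done via a telephone-administered survey" and "The 2- and 4-month visits will be completed via mail".

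**Analysis.** The outcome is a frequency of flares requiring treatment, and its baseline value is collected (Baseline study assessments, item 2). The Statistical Analysis text says: "For frequency of gout flares, analyses will also be adjusted for use of anti-inflammatory prophylaxis during initial ULT treatment". The general adjustment set is age, gender, income, alcohol, site and unspecified others. Poisson regression with allowance for over-dispersion is mentioned, but no outcome is attached to it. The longitudinal sentence begins "To analyze the longitudinal data (1-, 3-, 6-, 9- and 12-months), we will use mixed linear models for ULT adherence" and goes on to the serum urate target. It does not mention flares.

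**Benchmark.** The clinically meaningful change for flares is "20% fewer patients with gout flares needing treatment". The adherence row of the same table says that its difference is absolute. The flare row does not say.

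**The concern.** A flare count means something only with the period that it covers. Three places describe when flares are asked about, and they do not agree. The recall period in one of them depends on what counts as the last visit. Staff who follow different places would count flares over different stretches of follow-up.

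The analysis text then leaves open how unequal follow-up is handled. A count model without observation time treats a patient who left at month 4 like one followed to month 12. If the arms lose patients at different rates, the arm with more dropout appears to have fewer flares. Baseline flare frequency is usually a good predictor of later flares, and it is already collected, so leaving it out may give up precision at no saving.

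Finally, the outcome is a number of flares and the benchmark is a share of patients. A rate ratio alone cannot be set against that benchmark.

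**Working it through.** The plan gives no flare rate and no sample-size figure for flares, so there is nothing to reproduce. The check compares the texts and then illustrates the size.

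**1. Months of follow-up covered when recall runs from the last visit**

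| Flares asked at | Windows | Covered |
|---|---|---|
| Table 1: 1, 3, 6, 9, 12 | 0-1, 1-3, 3-6, 6-9, 9-12 | 12 of 12 |
| 12-month visit text: 3, 6, 9, 12 (last visit = in-person) | 0-3, 3-6, 6-9, 9-12 | 12 of 12 |
| Same, if the 1-month call counts as a visit | 1-3, 3-6, 6-9, 9-12 | 11 of 12 |
| Follow-up procedures: 6, 12 only (in-person visits also at 3 and 9) | 3-6, 9-12 | 6 of 12 |

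In the last row, months 0-3 and 6-9 are lost. Up to the 6-month primary time-point, 3 of 6 months are covered.

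**2. Bias without observation time when the true rate ratio is 1**

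Assumptions: a constant flare rate; a share d of an arm leaves by month 12, uniformly over the year. Mean observed time is then

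- to month 12: 12 × (1 − d/2)
- to month 6: 6 × (1 − d/4), because half of the leavers go before month 6, at month 3 on average.

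The apparent ratio is the ratio of the two mean times.

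| Dropout in the two arms | To month 6 | To month 12 |
|---|---|---|
| 20% and 20% | 5.70/5.70 = 1.00 | 10.8/10.8 = 1.00 |
| 15% and 25% | 5.625/5.775 = 0.97 | 10.5/11.1 = 0.95 |
| 10% and 30% | 5.55/5.85 = 0.95 | 10.2/11.4 = 0.89 |

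If the arms are exchanged, the ratios invert (1.03 and 1.05 at month 6; 1.06 and 1.12 at month 12).

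Simulation used 150 per arm (300 in total, equal allocation assumed), assumed 12-month means of 0.5, 1 and 2 flares, Poisson or negative binomial counts with dispersion 1, and a nominal 5% test. False-positive rates without an offset were about 5-6% (15%/25%) and 5-8% (10%/30%) at month 6, against 6-9% and 9-23% at month 12. With the offset, the rate is about 5%.

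**3. Precision from baseline flares**

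Simulation used 120 per arm (300 less 20%, halved), 12-month counts, between-patient variation with dispersion 1, and an assumed baseline look-back of 6 or 12 months. Adjustment lowered the variance of the log rate ratio by about 5-9%, 16-24% and 28-40% at means of 0.5, 1 and 2. If patients do not differ in their underlying rate, the gain is nil.

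**4. Two readings of the benchmark**

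If, say, 50% of controls had a treated flare, 20% fewer would mean 30% on the absolute reading (0.50 − 0.20) or 40% on the relative one (0.8 × 0.50).

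**The case against.** Much can be said for the plan, and most of it stands.

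- **The short schedule is not exclusive.** The parenthesis naming months 6 and 12 opens with the word including, and the 12-month visit text plainly has flares asked about at 3, 6, 9 and 12. A reader might infer that half of the follow-up will be lost. The documents do not support that: it happens only if staff take months 6 and 12 as the full list and also use recall since the last visit. But the parenthesis sits in a sentence about limiting burden, so that reading is possible.
- **The longitudinal month list does not settle the matter.** Its months match Table 1's flare months, but the sentence concerns adherence and serum urate. Table 1 has neither at month 1, so the list is weak evidence on the flare schedule.
- **The larger bias figures are not at the primary time-point.** A reader might take the 12-month ratio of 0.89, or a false-positive rate up to 23%, as the plan's risk. The primary time-point is 6 months, and 30% dropout in one arm exceeds the roughly 20% that the plan allows as its worst case. The control arm is attention-matched, and nothing in the documents predicts unequal dropout.
- **Baseline flares could enter as one of the other covariates.** The wording permits this but does not commit to it, and omission causes no bias in a randomised comparison.
- **The 20% figure is a benchmark.** A reader might treat it as a success criterion or a power claim. The plan makes it neither.

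**Conclusion.** The point holds as a minor one on a secondary outcome. Three places give flare schedules that must be reconciled, and one combination of them would count flares in only 6 of 12 months. The flare analysis leaves out observation time and a baseline value that is already collected, and the count model is not tied to flares.

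The bias from lacking an offset is small at month 6 (about 0.97 at 15%/25% dropout, 0.95 at 10%/30%), larger for a 12-month count (about 0.95 and 0.89), and nil if dropout is equal. These figures rest on assumed dropout shares and uniform timing. The loss from omitting baseline flares is one of precision only, and only if patients differ in their underlying flare rate. The open choice between absolute and relative is a matter of clarity. None of this touches the primary adherence outcome.

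**What to change.** 1. **Schedule.** Bring Table 1, the follow-up procedures and the 12-month visit text to one list of flare assessments. Run recall from the previous flare assessment instead of the last visit, so that the windows are contiguous and cover all follow-up whichever list is chosen.
2. **Model.** In the Statistical Analysis text, state that the number of treated flares from baseline to month 6 (main) and to month 12 (durability) is analysed by over-dispersed Poisson or negative binomial regression. Use log observation time as offset and baseline flare frequency as covariate, in addition to prophylaxis and the covariates already stated. Give the look-back period for the baseline frequency in the baseline assessments.
3. **Benchmark (minor).** Say whether the 20% is absolute or relative. As a supporting analysis, report the proportion with at least one treated flare by arm, with the matching risk difference or risk ratio and its 95% confidence interval.

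**Cost.** Wording and minor analysis work; no new contacts. If staff now ask only at months 6 and 12 and the longer list is kept, the 4 items at months 1, 3 and 9 add 4 × 3 = 12 items per patient, which works slightly against the aim of low burden.

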## Baseline study assessments.

After the patient has been consented and enrolled in the study, they will then complete the baseline patient assessments using VA Research Electronic Data Capture (REDCap) on IPad. Paper surveys will be used as a backup. Assessments will include the following:

- (1) Demographics: age, gender, income (covariates), marital status;
- (2) Baseline frequency of gout flares requiring treatment and baseline patient satisfaction with ULT treatment;
- (3) Baseline gout-specific HRQOL assessment using the gout assessment questionnaire (GAQ);
- (4) Alcohol use and BMI (covariates; exploratory outcomes since alcohol and higher BMI are associated with higher risk of incident gout, gout flares and higher sUA level (1, 26-28));
- (5) Blood draw for baseline sUA;
- (6) ULT non-adherence on self-reported questionnaire by Voils et al.;(29) and
- (7) Self-reported ULT use from non-VA sites (non-VA ULT use; sensitivity analyses). Patients' usual care serum urate values will be captured at this visit.

Additional information will be obtained including contact information, best time to contact and email address. Veterans will be provided with \$25 remuneration (VISA gift card or VA Form 10-7078 - Participant payment voucher) for completing study assessments at the screening and baseline visit. If payment voucher is used, participant will bring this voucher to agent cashier to receive \$25 on the same day. VA CDW and inpatient/outpatient SAS files assessed through the VINCI database. Medical records databases will be used to assess comorbidity, demographics (marital status) and baseline health care utilization and ULT medication adherence for the last 6-9 months (see eligibility criteria). Patients without DVD players will be provided with a DVD player to watch the DVDs at home at 2- and 4-months.

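### The plan does not say which SATMED-Q score is the satisfaction outcome or that its analysis uses the baseline score, and its two assessment schedules disagree

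*Combined protocol and SAP*

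**What the plan says.** The Outcomes section lists the second secondary outcome only as "Patient satisfaction with treatment". Table 1 names the instrument, the SATMED-Q, described as "17-item patient-reported with six dimensions", with assessments at months 0, 6 and 12. Its meaningful-change cell reads "Total score is between 5.9 and 13.4 and for SATMED-Q domain scores from 5.9 to 20.6", and continues "with most estimates close to 10.81". The other three rows of Table 1 each give a single value: 6% for adherence, and 20% each for flares and target serum urate.

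On timing, the follow-up section states: "The primary time-point for analyses will be at 6-months". The footnote to Table 1 uses the 12-month analyses, secondary outcomes included, to show whether effects seen at 6 months last. The description of the 12-month visit has patients report "patient satisfaction with treatment, as in 3-, 6- and 9-month follow-up".

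On analysis, Statistical Analysis gives adherence an unadjusted two-sample t-test at each visit and an ordinary least squares regression on age, gender, income, alcohol, site and unspecified further covariates. It then says: "Similar analyses will be conducted for the secondary outcomes defined in aim 2". Longitudinal models are named for adherence and for target urate, but not for satisfaction. Baseline study assessments includes "baseline patient satisfaction with ULT treatment" among the items collected.

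**The concern.** Three things are left open for this outcome.

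- **Which score.** The instrument yields a total and six domain scores. Table 1 gives criteria for both levels, and no section picks one. Nothing stops the choice being made after the results are known. The score is self-reported by patients who, according to the randomization section, know their arm, so a rule fixed in advance matters more here than for a laboratory value.
- **Whether the baseline score is used.** It is collected, but the t-test cannot use it and the regression does not name it. If it is left out, precision is lost that the trial could have from data already in hand.
- **When satisfaction is measured.** Table 1 and the 12-month visit text give different follow-up months, and sites cannot follow both.

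At stake is whether the satisfaction part of the second aim ends in one clear answer, estimated as precisely as the data allow.

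**Working it through.** The plan states no significance level, SATMED-Q standard deviation or error rate for this outcome, so there is no figure of its own to reproduce.

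**1. Number of scores.** From Table 1: 6 domains + 1 total = 7.

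**2. Chance of at least one false positive if all seven were tested at 6 months.** Assumptions: two-sided 5% per test, no true effect, and equal correlation between the six domain test statistics. The total is taken as the standardised sum of the domains. The quantity is P(any |z| > 1.96), obtained by simulation.

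| Scores tested | Assumed domain correlation | Chance of at least one false positive |
|---|---|---|
| One named score | not applicable | 5% |
| Seven | 0.7 | 16.4% |
| Seven | 0.5 | 20.8% |
| Seven | 0.3 | 24.5% (24.49% before rounding) |
| Seven | 0 (domains independent) | 28.2% |

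Seven fully independent tests would give 1 − 0.95^7 = 30.2%. That is an upper reference only, because the total is built from the domains.

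**3. Value of the baseline score.** With baseline-outcome correlation r, regression on baseline leaves a fraction 1 − r² of the outcome variance.

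- r = 0.3: 1 − 0.09 = 0.91, a cut of 9%.
- r = 0.5: 1 − 0.25 = 0.75, a cut of 25%.
- r = 0.7: 1 − 0.49 = 0.51, a cut of 49%.

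At r = 0.5 this is worth 1/0.75 = 1.33 times the patients. The comparison is with no adjustment. Against the adjusted regression already planned, the gain would be smaller to the extent that the listed covariates explain the same variation.

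**4. Schedules side by side.** Table 1 has follow-up at months 6 and 12. The 12-month visit text has 3, 6, 9 and 12. Months 6 and 12 are common to both; months 3 and 9 appear only in the visit text.

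**5. The meaningful-change cell.** The total has a range of 5.9 to 13.4 and the domains 5.9 to 20.6. The central value is printed as 10.81. Neighbouring cells of Table 1 carry reference numbers 78, 79 and 80, so this may be 10 followed by reference 81. That is an inference, and the cell does not say whether the value refers to the total, the domains or both.

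**The case against.** The strongest reply is that much of the freedom is only apparent. The plan fixes 6 months as the primary time-point, and the Table 1 footnote makes month 12 a check on whether a 6-month effect lasts. Table 1 lists satisfaction as one row, and no section says that the domains will be tested separately. The meaningful-change column serves interpretation: no planned analysis uses it as a pass mark, so a loose value there does not raise the false-positive rate. Baseline satisfaction could fall under the unspecified further covariates. The outcome is secondary, with no confirmatory claim attached.

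Most of this stands, and it rules out some stronger readings.

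- A reader might infer that any of seven scores at two or more visits could carry a claim, with error rates of 27% to 39% over months 6 and 12. The documents do not support this, because month 12 is not an alternative chance to succeed.
- A reader might infer that a difference of 8 points would count as both meaningful and not. It does lie between 5.9 and 13.4, but it falls short of the central value on either reading (10 or 10.81), and no decision depends on it.
- A reader might infer that the analysis ignores the baseline score. The text is silent; it does not exclude it.

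The reply does not settle which score is the outcome, whether baseline is in the model, or which schedule applies.

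**Conclusion.** The point holds as a gap in specification, together with an inexpensive improvement to the method. No section names the SATMED-Q total or a domain as the outcome, none says that the baseline score enters the analysis, and the two schedules conflict.

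The 16% to 24% describes what would happen if all seven scores were tested at 6 months. The plan does not announce that procedure, but neither does it rule it out. The figure rests on an assumed 5% level and assumed domain correlations of 0.7 to 0.3. The 9% to 49% variance reduction rests on assumed baseline-outcome correlations of 0.3 to 0.7. The absence of a named score and the schedule conflict need no assumption.

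Because satisfaction is a secondary outcome, this should be put right but does not threaten the primary result.

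**What to change.** In Table 1 and Statistical Analysis:

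1. Name the SATMED-Q total at the 6-month primary time-point as the satisfaction outcome, and label the six domains exploratory.
2. Analyse it by regression on arm, baseline SATMED-Q total and the covariates already listed, and state that this analysis decides.
3. Keep the 12-month sustenance analysis, with the same model.
4. Give one meaningful-change value for the total, with its source. The sponsor should confirm whether the printed 10.81 means 10 followed by a reference number, and whether it applies to the total.
5. Reconcile the months for satisfaction in Table 1 with those in the 12-month visit text.

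The cost is wording only: the baseline score is already collected, and no extra patients are needed. The downside is that a domain result could no longer be claimed as the satisfaction finding of the second aim.
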